5.10 Kit Preparation

Laboratory staff at the F.I Proctor Foundation will prepare the patient kits to be sent to the participant's residence. Each kit will include all materials necessary for the trial. The kit will include:

- The treatment allocation
- Swabs
- Cryogenic tubes with Zymo media
- Gloves
- Scissors
- Instructions for each swab collection procedure and patient handbook
- Parafilm
- Ziploc bags
- Category B Biological Substance Packaging for UN3373 materials
- Pre-paid shipping labels
- Patient Healthcare Provider Cards

The coordinator will sign out kits by scanning a barcode on a REDCap form when the kit is mailed to the patient. Study laboratory staff will sign in kits when they arrive from the participant. A barcode will once again be scanned into a REDCap form. Each kit will have a color coded sticker on the outside to identify which swab group the participant is in. The color scheme is:

Red: Group 1

Green: Group 2

Yellow: Group 3, Day 3

Blue: Group 3, Day 14

Blank: Group 4

Patient ID numbers will be generated by REDCap. The patient ID number will link the participant to the study questionnaires, treatment allocation, and swabs.

Each sample will be coded with a unique number. Swabs will be coded as a 6 digit number starting with a letter. For example, nasal swabs will be coded as N123456. Rectal swabs will be coded as R123456. Saliva swabs will be coded as S123456. These codes will also be generated by [name].

Healthcare provider cards will be provided in each kit. Participants will be instructed to provide this card to their healthcare provider in the event that they seek medical attention while in the study. The card will contain contact information that the provider may call to find out which medication, azithromycin or placebo, the patient has received as part of this study.

5.11 Drawing Prizes

A random drawing will be included in this study. The drawing will be open to all individuals in the study, individuals who are invited to participate in the study but decline, prospective subjects who are ineligible, subjects who withdraw from the study, and any individual who asks to be included. Winners will receive a gift card valued at \$100.00. We will select one winner after every 500 people are included in the drawing. Winners will be notified by telephone or email, and the gift card will be mailed to their home address.

The odds of winning will be about 1 in 500. We will continue to do the drawing throughout the time that we are recruiting participants for this study.

For any drawing, the odds of winning a prize depend on how many people are entered in the drawing. As we do not know how many people will participate in this study related drawing, we cannot predict what will be the odds of winning a prize.

5.12 Emergency Room Follow-Up

Participants who report an emergency room visit during their follow-up surveys will be re-contacted by the study team by phone or email. The participant will be asked to provide more detail regarding their emergency room visit. The study team member will ask the participant the primary reason for their emergency room visit, which interventions they received, and any other relevant information such as how long they were in the ER for. The participant's responses will be recorded in RedCap.

6 Sample Collection Procedures

6.1 Nasal Swab Collection

Willing participants will collect a self nasal swab on Day 3 of the study. A small group of 200 participants will be asked to collect a nasal swab at day 7 and day 14 too.

Participants will be instructed to:

1. Wash hands with soap and water.
2. Place the collection tube (labeled "NASAL") that is half-filled with clear liquid into the Styrofoam block and loosen but do not remove the cap.
3. Blow your nose to get rid of excess mucus.
4. Insert swab into one nostril, not too far, just so the cotton tip is inside your nose.

5. Rotate the swab against the nostril wall. Turn the swab a full 360° a total of two times.
6. Using the same swab, repeat steps 4 and 5 in the other nostril.
7. Open the tube and place the cotton end of the swab into the tube up to the marked line.
8. Break the swab stick by bending to snap the swab.
9. Put the cap back on the tube, making sure it is closed tightly and will not leak or spill and remove the tube from the Styrofoam block.
10. Gently stretch the parafilm around the seal on the tube. The film should stretch and stick to itself as you wrap the film around the tube.
11. Place the sealed tube back inside the provided kit bag and seal it shut.
12. Place the sealed kit bag into the provided biohazard bag.
13. Wash hands with soap and water.

6.2 Saliva Collection

Participants will also self collect a saliva swab on Day 3 of the study. The instructions will be included in the kit mailed to the participant's home. A small group of 200 participants will be asked to collect saliva at Day 7 and Day 14 as well. The instructions to collect a saliva swab are:

1. Wash hands with soap and water.
2. Place the collection tube (labeled "SALIVA") that is half-filled with clear liquid into the Styrofoam block and loosen but do not remove the cap.
3. Open the swab and place the cotton end of the swab beneath your tongue.
4. Keep the swab under your tongue for one (1) minute. Do not move the swab to other parts of the mouth.
5. Open the tube and place the cotton end of the swab into the tube.
6. Cut the swab using the provided scissors one finger width above the end of the cotton (~1 inch from cotton tip). See handout for scale (if needed). Allow the cotton end of the swab to gently fall the rest of the way into the tube. Dispose of the swab handle in the trash.
7. Put the cap back on the tube, making sure it is closed tightly and will not leak or spill and remove the tube from the Styrofoam block.
8. Gently stretch the parafilm around the seal on the tube. The film should stretch and stick to itself as you wrap the film around the tube.
9. Place the sealed tube back inside the provided kit bag and seal it shut.
10. Place the sealed kit bag into the provided biohazard bag.
11. Wash hands with soap and water.

6.3 Rectal Swab Collection

A rectal sample will be collected from a small subset of about 300 participants. The first 300 participants included in the study will be asked to collect a rectal swab during day 3 of the study. Additionally, a small group of 200 participants will be asked to collect a rectal swab at day 7 and day 14 as well. The steps for collection, processing, and storage include:

1. Take the provided swab package.

[figure not shown]
[figure not shown]
2. Position for the swab
 - a. The patient should stand in a squatting position.
3. Carefully remove the swab from the package and be sure the cotton tip is not touched.
4. Insert the tip of the swab into the patient's anus only as far as needed to make contact with fecal material (1 to 3 cm). Rotate the swab 180 degrees.
5. The tip should be a brownish color when removed from the patient.
6. Place the swab into the preservative into the collection tube. Be sure the swab is fully submerged in the liquid preservative and then break the swab off using the pre-scored breaking point.
 - a. If the swab cannot be broken off while the tip is fully submerged in the liquid, twirl the swab in the liquid first.
7. Tightly screw the cap back on the collection tube.
8. Wrap the area where the cap meets the tube with Parafilm to ensure the sample will not leak.
9. Place the tube in the rectal swab container.

All samples will be sent to the Coordinating Center. These samples are stored and shipped at ambient temperature using Category B Biological Substance shippers and pre-paid packaging slips. The instructions for shipping will be clearly marked in the instruction packet given to participants.

Packing Instructions:

1. Make sure the ULINE 6 cell absorbent sheet (white pouch) contains each of the samples you have collected. Make sure each sample is in a separate pouch. (See Figure 1).
2. Insert fully prepared absorbent sheet into the provided biohazard bag (See Figure 2).
3. Seal specimen bag by following instructions printed on the front of the bag.
4. Insert one sheet of the provided bubble wrap inside the bottom of the ULINE shipping box.
5. Place sealed biohazard bag should be placed on top of the bottom layer of bubble wrap.
6. Place the second sheet of bubble wrap on top of the sealed specimen bag.
7. Fold the top of the box down and insert each of the tabs into the sides of the box to fully close. (See Figure 5).

8. Seal the box with tape to make sure it does not open during shipping.
9. On top of the ULINE shipping box, remove or black out the old shipping label.
10. Take the new shipping label, provided with the kit and fill out your **NAME, ADDRESS, AND PHONE NUMBER** under the **FROM** section (Section 1). Be sure to press hard with a ballpoint pen. Everything else on the shipping label will be filled out for you.
11. Remove the top sheet of the shipping label to keep for your records. There should be two sheets remaining on the shipping label. **Do not remove the FedEx copy.**
12. Flip the label over and peel the backing off of the label. The back of the label should be sticky.
13. Stick the new label over the old label. Press down firmly on all corners to make sure it sticks.
14. Proceed to the shipping instructions to send your samples back to UCSF.

Shipping Instructions:

There are two ways to ship your samples back to UCSF. Each are described below:

1. Coordinator Assisted Shipping
 - a. Contact the **UCSF study coordinators** at **[contact]** or **[contact]**
 - b. The coordinators will take down your information and schedule a pickup at your house. Prepare to receive another call for further information about your samples' pick up.
2. Self-Schedule Shipping
 - a. Call **FedEx** at **[name]**
 - b. Say "schedule pick-up".
 - c. Say "I don't have an account number, use tracking number"
 - d. Continue scheduling a time that works for you. When you are finished, leave your package outside your door.
The total process should take five to ten minutes. If you are uncomfortable with this method please call the study coordinators instead as mentioned above.

7 Laboratory Procedures

All laboratory processing will be done at the conclusion of the trial. Samples will be de-identified. All laboratory personnel will be masked and samples will be processed in a randomized fashion.

Nasal swabs are placed in Zymo, which inactivated all infectious agents, including SARS-CoV-2. RNA will be extracted and subjected to RT-PCR to detect the E gene of SARS-CoV-2.

E Gene Primers and Probes

| | Sequence (5' to 3') |
|------------------|----------------------------|
| SARS-CoV-2 E Fwd | ACAGGTACGTTAATAGTTAATAGCGT |
| SARS-CoV-2 E Rev | ATATTGCAGCAGTACGCACACA |

| Probe | Sequence (5' to 3') |
|-----------------------|----------------------------|
| SARS-CoV-2_E_Prpb-FAM | ACACTAGCCATCCTTACTGCGCTTCG |

8 Duties and Responsibilities of Staff

8.1 Principal Investigators

The principal investigators of this trial are [name], PhD and [name].

- Develop study design, specific aims, and outcome measurements, with the help of the biostatistician, study coordinators, and partners
- Obtain grant funding with help of partners
- Ensure that the staff follow the protocol and properly execute all areas of research
- Ensure that all ethical approvals are maintained
- Write or add major contributions to all study-related publications
- Ensure proper masking procedures for staff involved in the study
- Supervise all aspects of the study

8.2 Co-Investigators

- Assume responsibility for the study in the absence of the Principal Investigators
- Supervise team members to ensure conformity to study procedures
- Assist in study design and development of statistical analysis plan
- Contribute to major decisions regarding the study

8.3 Study Coordinators

- Ensure the execution of the study per protocol
- Coordinate with outside laboratory sites
- Manage correspondence with participants
- Maintain all ethical clearances for the study, including IRB renewals, DSMC approvals, and FDA requirements
- Prepare all forms and documents needed
- Screen potentially eligible participants
- Collect informed consent from participants
- Arrange logistics for mailing participants their study kits
- Purchase, maintain, and organize study supplies
- Maintain communication and partnership with Principipl Investigators regarding all study activities and plans

- Appropriately back up forms and data

8.4 Biostatistician

- Create the statistical analysis plan (SAP)
- Prepare the randomization allocation list
- Receive all study data and review for quality control purposes
- Ensure appropriate masking
- Prepare data analysis plan for DSMC meetings, oversee analysis and prepare all presented data for DSMC meetings, reports, publications, and FDA reports.

8.5 Data Analyst

- Create and maintain the database for all collection and results related data for the study
- Monitor correct receipt of data after each collection visit
- Develop consistency checks in the data management
- Verify data inconsistencies with study coordinator
- Analyze and provide data regarding collection and results for study staff when needed, such as for publications, DSMC meetings, or other reports
- Back up all data appropriately
- Follow up on any missing data or lab results

8.6 Laboratory Technicians

- Prepare patient study kits with all materials needed for the study
- Organize study supplies
- Prepare patient information sheets and swab instructions
- Scan swabs received from the participants into the REDCap database
- Assist with laboratory analysis of samples
- Assist with biobanking and storage of specimens

9 Statistical Methods

Please see the Statistical Analysis Plan for details on pre-specified statistical methods for this trial.

The primary analysis will estimate the risk difference (RD) and risk ratio (RR) comparing azithromycin to placebo. We will estimate these parameters using a logistic regression model with a single covariate for treatment arm. We will estimate the RD and RR from the logistic regression using marginal standardization, and a bootstrap for 95% confidence intervals [5,6]. We will compute *P*-values for differences between arms using a permutation test with the difference between arms as the test statistic and 10,000 iterations.

The secondary analysis of viral load will compare log transformed values of relative read and number of reads using a t-test. We will compute *P*-values for differences between arms using a permutation test with the difference between arms as the test statistic and 10,000 iterations.

Determination of statistical significance for the primary and secondary analysis will follow the final alpha-spending function determined by the group sequential design.

10 Study Medication

The study drug product will be obtained from Pfizer, Inc. Participants enrolled in the study will be offered a dose of oral azithromycin or placebo determined by their randomization allocation. We will monitor adverse events following treatment as described in Chapter 9.

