3.4.2 Secondary Outcomes

Secondary outcomes will include

- **Hospitalization:** Defined as any visit to the emergency room or other hospital setting that resulted in a stay of 24 hours or more.
- **Adverse events:** we will conduct an adverse event survey at Day 3 after treatment, including gastrointestinal side effects (nausea, vomiting, diarrhea, abdominal pain) and rash. We note that some COVID-19 patients report gastrointestinal symptoms, and this survey will provide data on whether azithromycin causes additional gastrointestinal effects beyond those symptoms.
- **Prevalence of positive swabs:** we will compare the prevalence of SARS-CoV-2 positive swabs at Day 3 after treatment in self-collected nasal, saliva, and rectal swabs in azithromycin compared to placebo-treated participants.
- **Viral load:** we will assess viral load by RT-PCR in self-collected nasal, saliva, and rectal swabs at Day 3 after treatment.
- **Mortality:** we will collect emergency contact/next of kin information during the baseline questionnaire. We will follow-up with the emergency contact if participants are lost to follow-up at the Day 14 questionnaire to assess mortality and hospitalization outcomes.
- **Genetic macrolide resistance determinants:** We will evaluate the prevalence of genetic macrolide resistance determinants *ermB*, *mefA/E*, and *mphA* by targeted PCR in rectal samples collected at Day 3 after treatment.
- **COVID-19 symptoms:** we will ask patients about COVID-19 symptomology during each online questionnaire, including cough, fever, myalgia, anosmia, shortness of breath (and related abilities such as ability to walk across a room or up a flight of stairs), fatigue, conjunctivitis, and orthostatic symptoms.

- **Number of emergency room visits:** during each online questionnaire we will survey patients about any emergency room visits (with stays <24 hours) that occurred since their last survey.
- **Number of household members with COVID-19 (confirmed or symptomatic):** during each online questionnaire we will ask participants how many of their household members have symptoms of COVID-19 or confirmed disease.
- **Death:** we will attempt to link deaths among participants to the National Death Index.

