3.8 Main Study Timeline

| Timepoint | Activity |
|-----------|--|
| Day 0 | 
 • Eligibility Screening • Informed Consent • Baseline Questionnaire • Randomization |
| Day 1 | 
 • Treatment |
| Day 3 | 
 • Adverse events questionnaire • Self-collected nasal swab (opt-in) • Self-collected saliva swab (opt-in) • Self-collected rectal swab (opt-in) |
| Day 7 | 
 • Hospitalization and symptoms questionnaire |
| Day 14 | 
 • Hospitalization and symptoms questionnaire (primary endpoint) |
| Day 21 | 
 • Hospitalization and symptoms questionnaire |

4 Chapter 3: Study Eligibility

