4.1 Inclusion Criteria

Participants must meet the following inclusion criteria to be eligible for this study:

- Evidence of a positive SARS-CoV-2 test and test results received within the previous seven days
- Not currently hospitalized
- Willing and able to receive study drug by mail
- Willing and able to return the internet-based study questionnaires at baseline, day 3, 7, 14, and 21 days via email or over the phone.
- No known allergy or other contraindication to macrolides
- No known history of prolongation of the QT interval (eg. History of torsades de pointes, congenital long QT syndrome, bradyarrhythmia).
- No recent use of hydroxychloroquine within the past 7 days for participants >55 years of age.
- Not currently taking nelfinavir or warfarin (Coumadin)
- Age 18 years or older at the time of enrollment
- Not currently pregnant
- Provision of informed consent

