### 3.2. Randomization

Participants will be randomized 2:1 to either receive a dose of oral azithromycin or oral placebo. Patients will be twice as likely to receive azithromycin than placebo. The randomization will not be stratified or blocked in any way. We found that even with permuted block sizes and  $\geq 6$  labels (4 azithromycin, 2 placebo), a 2:1 allocation could lead to unmasking through longer runs of active treatment labels.

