### **5.5. Baseline patient characteristics**

We will summarize patient characteristics by arm, including: age, sex, location (to level of US state), and clinical symptoms at the time of enrollment.

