### 6.2. Analysis methods

#### Primary Outcome:

The primary analysis will estimate the risk difference (RD) comparing the proportion of patients who are symptom-free at 14 days in the azithromycin versus placebo arms. We will compute *P*-

values for differences between arms using a permutation test with the prevalence difference between arms as the test statistic and 10,000 iterations. We will additionally estimate and report the prevalence ratio.

Determination of statistical significance for the primary and secondary analyses will follow the final alpha-spending function determined by the interim analyses (see section 3.5).

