## **6.4. Additional analyses**

### **Pre-specified Subgroup Analyses**

In secondary analyses, we will estimate differences separately by the following subgroups:

- Age >60 versus ≤ 60
- “High risk” versus low risk patients, with “high risk” defined as Age >60 and reported hypertension, cardiovascular disease, diabetes, or obstructive or restrictive lung disease at enrollment.
- Presence of COVID-19 symptoms at enrollment versus asymptomatic at enrollment.

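### Optional efficiency gain: the unadjusted primary analysis is valid, but adjusting for symptoms at enrollment, which are already collected, would make it slightly more precise

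*Protocol*

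**What the plan says.** **Primary analysis.** Protocol section 9 fits a logistic model for the risk difference and risk ratio: "We will estimate these parameters using a logistic regression model with a single covariate for treatment arm". It adds marginal standardization, bootstrap intervals and a permutation P-value. SAP 6.2 (Primary Outcome) estimates the "risk difference (RD) comparing the proportion of patients who are symptom-free at 14 days in the azithromycin versus placebo arms", with a permutation test on that difference. It names neither a model nor a covariate.

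**Design.** SAP 3.2: "The randomization will not be stratified or blocked in any way". No stratification factor has therefore been left out of the model, and the design does not balance baseline symptoms.

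**Baseline symptoms.** Protocol 3.4.2 says "we will ask patients about COVID-19 symptomology during each online questionnaire". The Protocol 3.8 timeline puts the "Baseline Questionnaire" on Day 0 and treatment on Day 1. SAP 5.5 summarizes "clinical symptoms at the time of enrollment" by arm.

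**Asymptomatic entrants.** The Protocol 3.2 profile describes people with mild or moderate symptoms. The listed criteria do not require symptoms; the disease criterion in Protocol 4.1 is "Evidence of a positive SARS-CoV-2 test and test results received within the previous seven days". SAP 6.4 pre-specifies the subgroup "Presence of COVID-19 symptoms at enrollment versus asymptomatic at enrollment".

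**Adjustment elsewhere.** SAP 6.3 has a doubly robust sensitivity analysis with enrollment symptoms among its covariates, run if more than 15% of outcomes are missing. Protocol 15.4 mentions adjusted analyses in the closed reports to the monitoring committee and names no covariates.

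**The concern.** The outcome is absence of a list of symptoms at Day 14. The natural predictor is presence of the same symptoms at enrollment, and the plan collects it without using it in the primary estimate. With arm as the only term, marginal standardization simply returns the two crude proportions, so the Protocol's method does no more than a direct comparison.

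At stake is the width of the interval around the trial's main result. The outcome and sample size were revised because enrollment was slow and hospitalization was rare, so precision is scarce. Neither the subgroup estimates, nor the conditional sensitivity analysis, nor the closed-report adjustments make the primary estimate more precise.

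**Working it through.** **Inputs from the documents.** N = 455, 2:1 allocation, 50% versus 65%, 20% loss (SAP 3.3). Final test at two-sided 0.049 (Protocol 3.5; SAP 3.5 gives one-sided 0.0245), critical value 1.969.

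**Assumed, not in the documents.** The share *a* without symptoms at enrollment, and the probability *q* that such a person is symptom free at Day 14 on placebo. The odds ratio for treatment is taken as common to both groups.

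**1. The plan's own figure.** Pooled proportion = (0.50 + 2 × 0.65)/3 = 0.60. Placebo n = [1.960 × √(0.60 × 0.40 × 1.5) + 0.8416 × √(0.25 + 0.2275/2)]² / 0.15² = (1.1760 + 0.5076)² / 0.0225 = 125.97. Multiplying by 1.20 gives 152 placebo and 303 azithromycin, total 455, as in the SAP table.

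**2. Unadjusted power.** Outcomes: 455 × 0.8 = 364, that is 242.7 azithromycin and 121.3 placebo. Variance = 0.2275/242.7 + 0.25/121.3 = 0.002998; SE = 0.0548. Power = Φ(0.15/0.0548 − 1.969) = 78.0%.

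**3. Adjusted power.** Variance = average within-stratum binomial variance in each arm divided by that arm's size, plus the variance of the stratum risk differences divided by 364.

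Example, a = 0.10 and q = 0.90:
- Placebo probability in the rest: (0.50 − 0.09)/0.90 = 0.4556.
- An odds ratio of 1.927 gives 0.9455 and 0.6172 on azithromycin, averaging 0.65.
- Within-stratum variances: 0.2178 (azithromycin) and 0.2322 (placebo).
- Variance = 0.2178/242.7 + 0.2322/121.3 + 0.000003 = 0.002815; SE = 0.0531.
- Power = 80.5%. Variance ratio = 0.002998/0.002815 = 1.065, worth 364 × 0.065 ≈ 24 outcomes.

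| Asymptomatic at enrollment | q = 90% | q = 70% | q = 50% (not prognostic) |
|---|---|---|---|
| 5% | 79.1% | 78.3% | 78.0% |
| 10% | 80.5% | 78.6% | 78.0% |
| 20% | 83.7% | 79.5% | 78.0% |

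In the 90% column the gain is worth about 11, 24 and 58 outcomes. At 5% asymptomatic the 95% CI half-width falls from 10.73 points to 10.58 (q = 90%) or 10.69 (q = 70%).

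**4. The permutation test.** This was simulated with 364 outcomes, 8,000 trials and 999 permutations each, refitting the adjusted model every time. At a = 0.10 and q = 0.90, power goes from 76.0% to 79.8%. With a non-prognostic covariate (q = 0.50) it still goes from 76.4% to 77.9%. These 1.5 points arise because the crude statistic has many ties, which makes its permutation test slightly conservative. They are not a prognostic gain, so the closed-form figures are the ones to quote.

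**5. Validity.** In the same simulation, type I error at nominal 4.9% (a = 0.10, q = 0.90) was 4.3% crude and 5.0% adjusted, with Monte Carlo SE 0.24 points. The mean risk difference was 0.149 to 0.151 for both estimators, so the marginal estimand is kept.

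**6. Sparse categories.** Take a = 0.05 and q = 0.90, with 0.944 symptom free on azithromycin. An asymptomatic entrant has symptoms at Day 14 with probability (2/3) × 0.056 + (1/3) × 0.10 = 0.070. The chance that no such person is observed is (1 − 0.05 × 0.070)ⁿ, about 53% at 182 outcomes (the interim) and 28% at 364. The logistic model then has separation.

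**The case against.** **Nothing is wrong with the planned analysis.** A reader might infer that leaving out a prognostic covariate, under unstratified randomization, biases the result or inflates type I error. The documents do not support that. Simple randomization makes the crude comparison unbiased and its permutation test valid. With losses it also needs outcomes missing completely at random, which SAP 6.3 states. An unadjusted primary estimate is a legitimate choice. This objection stands and makes the point optional.

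**The gain may be negligible.** Protocol 3.2 describes a symptomatic population. The criteria and the subgroup allow asymptomatic entrants but do not show that many enroll. This stands too: the 83.7% figure needs 20% asymptomatic together with a 90% outcome.

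**Adjustment is already planned.** At the SAP's assumed 20% loss, the 15% trigger in SAP 6.3 would be met, so an adjusted sensitivity analysis would run. That largely covers a supportive adjusted result, but it leaves the primary estimate as imprecise as before.

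**The covariate may not be pre-treatment.** Protocol 5.2 emails the baseline form in the same step as the drug is mailed, and Protocol 5.9 has reminders running to a call at 3 days. A late form could follow dosing. This is a fair objection, and the amended text needs a rule for it. Separation (step 6) needs one as well.

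**Credibility.** The primary outcome was changed in December 2020. A second change to the primary analysis, for what may be about one power point, has a price. This stands and is for the sponsor to weigh.

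**Conclusion.** This is a cheap, optional improvement in efficiency. The unadjusted risk difference may stand as it is.

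The likely gain is between 0 and 2.5 power points (78.0% to at most 80.5% with 10% or fewer asymptomatic). It rests on two figures the documents do not give, the asymptomatic share and its Day 14 outcome, and on a common odds ratio. The power figures are for the final test alone.

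Two further inferences go too far. Adjustment is not a remedy for sample size: it adds no participants, and its yield cannot be known from the documents. Nor does it undo dilution by people who were already symptom free at entry.

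**What to change.** If the sponsor wants the gain, put the same text in Protocol 9 and SAP 6.2 before any comparison by arm:

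> The primary RD and RR are marginally standardized from a logistic model with arm and one main-effect covariate: any versus no SAP 6.1 symptom at enrollment, using only baseline answers recorded before the study drug was taken. Unanswered or later answers form a third category. 95% CIs are by bootstrap. The P-value uses the adjusted RD as test statistic, with the model refitted in each of 10,000 permutations. If a covariate category has all or no outcomes, or the model does not converge, a penalized (Firth-type) fit is used in the data, every bootstrap and every permutation. The unadjusted RD is supportive.

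A stratum-weighted RD could replace the penalized fit, provided one of the two is named in advance. The drug date comes from the Day 3 questionnaire (Protocol 10.7), so the coding rule should also say how a form completed on the day of dosing is classed. The third category is needed because participants may skip questions (Protocol 12.3). The sparse-category rule was not part of the simulation and should be tested before adoption.

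The documents do not say whether the interim comparison has taken place. If any comparison by arm has been seen, keep the unadjusted RD as primary and report the adjusted RD as supportive.

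**Cost.** A second mid-trial amendment to the primary analysis after December 2020, one coding rule, and slightly more complex code. The text would also align the two documents, since SAP 6.2 does not now name the model or the interval method.
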